#### **C 16. Implications and Future Directions**

Few experimental implementation studies have been conducted. Findings from this proposal have the potential to: (1) yield a robust theoretical and practical model delineating contextual factors and

evaluative processes for implementation in an academic-community partnership; (2) demarcate the benefit of using standardized versus tailored protocols for implementation; (3) establish a blended protocol for MBC implementation with capacity for generalization to community mental health centers nationwide; and, (4) highlight contextual factors responsible for sustained MBC implementation. With depression maintaining its place among the nation's top chronic illnesses, costing billions of dollars annually, positive findings from this proposal will present a feasible and effective approach to alleviating great societal burden through a minimal intervention needed for change. This study will lay the groundwork for subsequent research (by establishing progress monitoring) to enhance usual care for multi-problem clinical presentations, should MBC effects plateau and additional interventions be necessary.

### SECTION I: STUDY DESCRIPTION

A. Please describe (in lay terms) the general objective(s) of the proposed research, including research question(s), hypothesis, and a short summary of the main interactions/interventions. If appropriate, describe any usual methods, that were considered, but not chosen, and why.

Depression remains among the nation's top 10 chronic illnesses, costing over \$80 billion annually. Depression has been called the "Common Cold" of mental illness, but one with serious risk of morbidity and mortality. There are now many evidence-based practices for the treatment of depression, but unfortunately these practices remain largely unavailable to clients receiving services in community mental health centers. Measurement Based Care (MBC) is a relatively simple evidence-based intervention framework. MBC, by definition, is the practice of using symptom measurement to inform mental health care. Physicians who routinely measure the patient's blood pressure when the treatment target is high blood pressure demonstrate the medical corollary of MBC. When MBC is used in the treatment of depressed adults, it has been shown to improve outcomes by identifying clients who are not making progress and reducing the likelihood that clients will deteriorate in treatment. However, despite the demonstrated effectiveness of MBC, the majority of community mental health counselors (i.e., clinicians) do not regularly assess target problem symptoms to guide their work over the course of treatment. To our knowledge, no studies to date have focused on the process of implementing MBC in community mental health settings. The long-term goal of this research project is to provide generalizable and practical recommendations about implementation approaches that promote MBC use and fidelity in community mental health centers. Specifically, this study will test a standardized versus a tailored approach to implementing MBC in one of the nation's largest not-for-profit providers of behavioral health services. Although touted as superior, tailored implementations have rarely been compared to standardized approaches. Moreover, recent research has demonstrated an apparent need to adapt evidence-based practices to fit the specific context in which they are being implemented, particularly if they are to be sustained. This proposal reflects a movement in the field of implementation science in which planned adaptations are being tested and compared to standardized versions. The proposed research is a three-phase, mixed methods (quantitative/qualitative) study to investigate the effect of these two different approaches to MBC implementation on both clinician-level (e.g., MBC fidelity) and client-level (depression symptom change) outcomes. We will focus on contextual factors (e.g., attitudes, resources, process, etc.) that may influence the implementation process with the goal of identifying a generalizable and practical way of bringing MBC to community mental health centers treating depressed adults.

### SECTION V: SUBJECT POPULATION

A. **Subject Population.** Check all subject population categories below for which there is a reasonable expectation of enrollment into this research study:

- Children** (Complete the Request Form for the Inclusion of Children in Research)
- Cognitively Impaired** (Complete the Request Form for the Inclusion of Cognitively Impaired Individuals in Research)
- Economically/Educationally Disadvantaged**
- Pregnant Women, Human Fetuses, or Fetal Material** (Complete the Request Form for the Inclusion of Pregnant Women, Human Fetuses, and Neonates in Research)
- Prisoners** (Complete the Request Form for the Inclusion of Prisoners in Research)
- Subjects Outside of U.S. Targeted for Enrollment** (Complete the Transnational Research Information Form)
- Veterans** or research funded by the VA, utilizing VA effort, property or resources, or enrolling VA patients. (Complete the Request Form for VA Research)
- Students.** When there is a teacher-student relationship dynamic, complete the following questions:

B. **Inclusion/Exclusion.**

#### Clinicians

*Inclusion Criteria.* Clinicians will be eligible for the study if they: 1) provide individual psychotherapy; 2) provide psychotherapy to adults with depression (based on their self-reported typical and current caseload (i.e., clinicians will learn in the eligibility

discussion that if they consent to participate in the study then they must have eligible clients to potentially enroll as well); 3) conduct psychotherapy sessions in English.

**Exclusion Criteria.** Clinicians will be excluded if they indicate during enrollment that they intend to leave the organization and will be unable to complete all study phases.

### **Clients**

**Inclusion Criteria.** As this is a pragmatic trial (Thorpe et al., 2009), clients will be eligible for the study if they: 1) are age 18 and above; 2) have depression as one of the primary treatment foci: diagnosis will be made by clinicians using usual care interview methods and can include any of depressive disorder diagnosis (e.g., major depressive episode, dysthymic disorder); 3) have significant depressive symptom severity (PHQ-9 total score > 9 at intake); 4) will receive individual psychotherapy; 5) are receiving psychotherapy treatment with an enrolled clinician during the proposed funding period.

**Exclusion Criteria.** Because of the pragmatic nature of this trial, there is only one exclusion criterion for clients. Specifically, clients will be excluded if they are unable to provide verbal consent due to severe mental illness or inability to read, for instance.

### **Administrators**

**Inclusion Criteria:** Administrators must have some sort of administrative role at the site or as part of Centerstone as a whole. However, the position they must have an administrative role within one of the twelve sites that will be participating in project.

**Exclusion Criteria:** The only exclusion criteria are that 1) the administrator must be involved with one of the twelve sites participating in the project. Those who have an administrative role in one of Centerstone's other sites will not be eligible to participate. 2) Those who indicate they intend to leave the organization and will be unable to complete all study phases will not be eligible.

### **Office Professionals**

**Inclusion Criteria:** Office professionals must have a role at one of the twelve participating Centerstone sites.

**Exclusion Criteria:** The only exclusion criteria are that 1) the office professional must be involved with one of the twelve sites participating in the project and 2) those who indicate they intend to leave the organization will be unable to complete all study phases will not be eligible.

### **Staff**

**Inclusion Criteria:** Staff must provide services to the client at one of the 12 participating Centerstone sites or provide support to another staff member providing services to the client. Depending on the site, staff could include but is not limited to nurses, doctors, psychiatrists, and case managers.

**Exclusion Criteria:** The only exclusion criteria are that 1) the staff must be involved with one of the twelve sites participating in the project and 2) those who indicate they intend to leave the organization will be unable to complete all study phases will not be eligible.

## **C. Number of Subjects.**

### **Clinicians**

Clinicians will be recruited from 12 Centerstone sites across two states (Indiana and Tennessee). Approximately 187 clinicians (average of 16 per site) will be recruited during the latter half of Phase 1 of the study (months 5 to 8) to achieve our target enrollment of 150 (accounting for clinician turnover) and allow for initial site randomization (to early or late and standardized or tailored implementation) to occur just prior to Phase 2 (months 8-38).

### **Clients**

Clients seeking treatment for depression at the 12 enrolled Centerstone sites will be recruited for participation in the proposed research during Phase 2 of the study (months 8 to 38; we will stop recruitment at month 35 to allow for the necessary 12 week assessment to be completed during Phase 2). Approximately 625 clients will be recruited (given the potential for unplanned attrition) to achieve our goal enrollment of 500 clients (an average of 42 per site, 3 per clinician) based on power analyses.

### **Administrators**

Administrators will be recruited from the 12 enrolled Centerstone sites across two states as well as those who have a larger role within Centerstone, such as the executive director. About 12 administrators (about 1 per site) will be recruited during the latter half of Phase 1 of the study (months 5 to 8) to participate in individual interviews and then later implementation team meetings.

### **Office Professionals**

Office professionals will be recruited from the 12 enrolled Centerstone sites across two states. Approximately 12 office professionals (about 1 per site) will participate in the implementation team meetings.

### **Staff**

Staff will be recruited from the 12 enrolled Centerstone sites across two states. Approximately 300 staff members will participate by completing small batteries of questionnaires.

## SECTION VII: STUDY PROCEDURES

The study consists of three main phases each is described briefly below.

Phase 1: Start up/Pre-Implementation (months 0-8) will interface the most widely used and validated depressive symptom severity measure (Patient Health Questionnaire-9 item; PHQ-9; [name], 2001) with the electronic health record. Enrollment of clinician, administrators, office professionals, and client participants will begin. Randomization at the site level will occur to one of the two conditions, standardized or tailored implementation of measurement-based care for depression. In addition, sites will be randomized to early and late stage implementation across 4 cohorts (2-4 sites in each cohort), with each cohort having 5 months of active implementation and 10 months of sustainment monitoring.

Phase 2: Randomized Trial: Implementation & Sustainment (months 8-38) constitutes the active implementation (5 months) of measurement based care and sustainment (10 months) phase. Clinician, administrator, office professional, staff, and client participation will occur during this phase.

Finally, phase 3: Post Hoc Characterization of MBC Fidelity, Analysis and Manuscript Preparation (38-48 months) will consist of post-hoc characterization of measurement-based care fidelity (MBC fidelity; Appendix B.2), defined as (a) client completion of the PHQ-9, (b) clinician review of scores in the electronic health record, and (c) discussion of scores in session.

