## **C. APPROACH**

**Overview.** Given the underwhelming use of MBC in community mental health settings coupled with the demand for performance outcome assessment (Affordable Care Act), this randomized implementation trial aims to compare the effectiveness of a standardized versus tailored approach to implementation of MBC with co-primary outcomes at the clinician (MBC fidelity) and client (depression severity) levels. We will randomize 12 sites of a large community mental health center (Centerstone) to early or later stage standardized or tailored implementation enrolling 150 clinicians and 500 depressed clients in a pragmatic trial (Thorpe et al., 2009). The main clinician level outcome is MBC fidelity, defined as (a) client completion of the PHQ-9, (b) clinician review of scores in the electronic health record, and (c) discussion of scores in session. Phase 1 (months 0-8) will interface the most widely used and validated depressive symptom severity measure (Patient Health Questionnaire-9 item; PHQ-9; [name], 2001) with the electronic health record; this measure is the main client level outcome. Phase 2 (months 8-38) constitutes the active implementation (5 months) and sustainment (10 months) phase. In both conditions, clients will have the option to complete the PHQ-9 on tablets in the waiting room prior to session, which will feed scores to clinicians via the electronic health record. Sites randomized to the standardized condition will begin with a baseline mixed methods needs assessment (for the purposes of putative mediator data collection) and receive the guideline that MBC is to be used in each session with a depressed client. The standardized condition will include manualized training and triweekly group consultation with experts to promote MBC fidelity and optimize its clinical utility. An implementation team (including a site administrator, opinion leader, MBC champion, and research personnel) will convene prior to each triweekly group consultation to review progress and troubleshoot problems. Sites randomized to the tailored condition will also begin with a needs assessment to identify contextual factors that may serve as barriers to the implementation (guided by the *Framework for Dissemination*; [name] et al., 2008; see C7). Training and triweekly group consultation will be tailored to address these barriers (e.g., clinician attitudes toward MBC). The implementation team (same composition as in standardized) will define a site-specific guideline for MBC use (e.g., monthly) and convene prior to each triweekly group consultation to troubleshoot MBC fidelity barriers. At the start of the active implementation across both conditions, depressed clients of participating clinicians will be enrolled to compare the effect of standardized versus tailored MBC implementation on client outcomes. Phase 3 (months 38-48) will characterize MBC fidelity using electronic health record data capture. The evaluation approach is guided by the *Framework for Dissemination* ([name] et al., 2008) and includes a baseline needs assessment, implementation/process evaluation (5 months into implementation), and outcome/impact evaluation (15 months into implementation). This design will allow for a direct test of the assumption that voltage drop in treatment outcomes occurs in the context of adapting the intervention to fit the context (Chambers et al., 2014), while simultaneously exploring the effect of standardized and tailored approaches to MBC implementation.

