**Phase 2: Randomized Trial: Implementation & Sustainment.** Implementation will take place across 12 sites in months 8-38 using the dynamic waitlist control design (Brown et al., 2006; C15. Justification and Feasibility). Specifically, matched sites (based on size and urban/rural status) will be randomized to either early or later stage implementation in 4 cohorts (2-4 sites per cohort spaced 5 months apart), with half the sites randomized to the standardized and half to the tailored condition; see Figure 2 for a concise depiction of the implementation timing. The timing of this protocol is based on the published work of Miller et al. (2012) as well as the successful naturalistic MBC implementation at Group Health (personal communication, [name], February 11, 2014). Beginning at month 8, the earliest cohort (2 sites) will engage in the baseline mixed methods needs assessment (Assessment Time 1; AT1). Using purposeful sampling (Palinkas et al., 2013), a subset of clinicians (N=5-8 at each site) representing extreme variation (nominated by clinic directors based on their support for or against MBC implementation) will participate in a 1.5-hour focus group. This sampling approach is critical to gain a wide range of clinician views. Rapid ethnography will then be used to uncover site-specific insights that will guide the content of training and consultation in the tailored condition only (with the aid of mixed method expert [name]; C13b. Data Analysis Plan). During the needs assessment, all enrolled clinicians will complete the battery of baseline measures (see Table 5, Section II), from which the opinion leader (Childers, 1998) and self-nominated MBC champion will be identified and invited to join the implementation team. Across conditions, this team will convene triweekly during the 5-month active implementation period to ensure implementation strategy fidelity (Proctor et al., 2013) and review MBC fidelity. Following the needs assessment, clinicians will participate in a 4-hour MBC training workshop (see C9. Pilot Studies for content) and will begin triweekly consultation. To characterize the differences in implementation team meetings and consultation between conditions, sessions will be audiorecorded and contextual factors logged by graduate research specialist on the MBC Barriers Log (informed by the Framework for Dissemination; [name] et al., 2008; see Appendix for form template). Simultaneously a site team member will log meetings (using the same form) and data triangulated to calibrate site team members and prep for the exit of research personnel. Implementation/Process Evaluations ([name] et al., 2008; AT2) at the clinician level will occur 5 months after the needs assessment at which point the research personnel will be removed. The site implementation teams will be encouraged to continue meeting to promote MBC sustainment and the responsibility to log and address MBC barriers will transfer completely to the site team members. Outcome/Impact Evaluation ([name] et al., 2008; AT3) at the clinician and client level will occur 10 months after the Implementation/Process Evaluation. Focus groups will be held with the implementation team at AT3 to review their experience and the site's progress since the research personnel exited the team. All aforementioned steps will be repeated across the remaining three cohorts.

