### C12b. Depressed Adult Clients

**Recruitment.** Adult clients ( $N=625$ ; target  $N=500$ ) seeking treatment for depression at Centerstone will be eligible for enrollment in the research study. As this is a pragmatic trial (Thorpe et al., 2009) client participation criteria include: (a) age 18 and above; (b) depression is one of the primary treatment foci based on diagnosis made by clinicians using usual care interview methods to reflect major depressive disorder, dysthymic disorder, depressive disorder NOS, adjustment disorder with depressed mood; (c) significant depressive symptom severity (PHQ-9 total score  $> 9$ ); (d) receipt of individual psychotherapy; (e) fluency in English; and, (f) new client beginning treatment (g) with an enrolled study clinician during the proposed funding period. Exclusion criterion is minimal: an inability to sign the consent due to lack of competence or inability to read. Intake clinicians will be trained to identify eligible clients and assess if they would be interested in hearing more information about a research study. If the client agrees, the clinician will share the client's contact information with the project coordinator. Because Centerstone has a strong research commitment, clinicians and clients are accustomed to a research environment where the option to participate in studies is more routine than in many community mental health centers. Both Centerstone clinicians and clients have participated in a number of research studies and recruitment is expected to be very straightforward. However, to supplement this approach, Co-I ([name], Director of Centerstone Research Institute) will run weekly queries of the Centerstone database (in accordance with Health and Human Services guidance) to identify eligible clients (see Human Subjects for previously used HIPAA compliant procedures) who will be contacted by our project coordinator to assess interest in study participation. Once a client has been enrolled, the study team will flag the client in the electronic health record to initiate study procedures for the clinician. Given the number of clients seeking treatment for depression at Centerstone ( $> 30,000/yr$ ), we anticipate that our client recruitment goal will be feasible.

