### **Clients: Across Both Conditions (i.e., Standardized and Tailored)**

#### **Phase 1 (Months 0-8)**

*Pre-Implementation.* A research assistant will contact potentially eligible clients via telephone and will perform an initial 10-20 minute phone screen to assess eligibility (RCR.3). A telephone version of the Patient Health Questionnaire-9 (PHQ-9; Appendix C.2) will be performed during the phone screening with the Centerstone Research Institute research assistant (CRI RA) in both conditions. This questionnaire should only take about five minutes to complete and clients will receive a \$5 incentive for completing the PHQ-9 regardless of their study eligibility. The client is deemed eligible if the client indicates that depression is a primary focus of treatment, s/he is seeking treatment with an enrolled study clinician, and s/he scores a 9 or higher on the PHQ-9. If the client is eligible, s/he will be asked to respond to a Client Demographics Questionnaire (Appendix C.1) over the phone during this initial screen. The data obtained from the initial PHQ-9 screen (RCR.3) and demographics questions is to be collected, labeled with a 9-digit anonymous research ID, and kept in a secure database in the secure server at Centerstone. If s/he is eligible and interested in participating, s/he will be asked to give verbal consent to participation over the phone during the initial screen conducted by the CRI RA. The CRI RA will also offer to call the client back if s/he would like time to review the informed consent statement before agreeing to participate. After a client verbally consents to participation or indicates that they would like time to review the consent statement, a

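### The documents conflict on when client enrolment opens, so clients at later-cohort sites could be enrolled, and counted under their assigned condition, before their site implements anything.

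*Combined protocol and SAP*

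**What the plan says.** The combined protocol and SAP gives several rules for when clients may enter.

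- **Phase 1.** Section VII, in its summary of months 0 to 8, says "Enrollment of clinician, administrators, office professionals, and client participants will begin". The client procedures in Section VII, under their own Phase 1 pre-implementation heading, add "A research assistant will contact potentially eligible clients via telephone and will perform an initial 10-20 minute phone screen to assess eligibility".
- **Funding period.** C12b requires only that the client be treated "with an enrolled study clinician during the proposed funding period". The client inclusion criteria in Section V.B set the same limit.
- **Start of active implementation.** Section C, Overview: "At the start of the active implementation across both conditions, depressed clients of participating clinicians will be enrolled". C10 describes active implementation as a five-month period belonging to each site.
- **Study-wide window.** Section V.C says clients "will be recruited for participation in the proposed research during Phase 2 of the study", and "we will stop recruitment at month 35 to allow for the necessary 12 week assessment to be completed during Phase 2". It gives no opening date by site or cohort.

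Sites start in four cohorts, "2-4 sites per cohort spaced 5 months apart", the first of them with two sites at month 8 (C11, Phase 2). C13a applies intention-to-treat by assigned condition. Its depression model contains time, patient status, implementation group, session counts and counts of PHQ-9 use.

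**The concern.** A client whose treatment falls before the site's start date receives care that neither implementation approach has yet touched. In expectation such clients show no difference between standardized and tailored sites, whatever the true effect. If they are analysed under their site's assigned condition, they pull the estimated client-level difference towards zero, and that difference is one half of the co-primary aim.

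Nothing in the analysis plan would reveal or correct this. New versus existing patient status describes the client's treatment history and does not show whether the site had started. The recruitment procedure would not prevent it either. Section XII has research assistants query the record system daily for clients of enrolled clinicians, and C12a enrols clinicians at all sites in months 5 to 8. The readable text contains no step that holds recruitment at a later-cohort site until that site starts.

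**Working it through.** **Timeline, reproduced first.** Inputs from C11: first cohort at month 8, cohorts 5 months apart, 5 + 10 = 15 months each.

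- Starts: 8 + 5k for k = 0 to 3, giving months 8, 13, 18 and 23.
- Ends: start + 15, giving months 23, 28, 33 and 38. The last matches the stated end of Phase 2.
- 12 weeks is about 2.76 months, and 38 − 2.76 = 35.2, which matches the stated recruitment stop at month 35.

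**Share recruited before site start.** Assume even accrual at all 12 sites over months 8 to 35, which is 27 months. By cohort, (start − 8)/27 gives 0/27 = 0%, 5/27 = 18.5%, 10/27 = 37.0% and 15/27 = 55.6%.

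Cohorts hold 2 to 4 sites and the first holds 2, so the extreme splits of the 12 sites are 2, 4, 4, 2 and 2, 2, 4, 4.

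- 2, 4, 4, 2: (4 × .185 + 4 × .370 + 2 × .556)/12 = .278, or 139 of 500.
- 2, 2, 4, 4: (2 × .185 + 4 × .370 + 4 × .556)/12 = .340, or 170 of 500.

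**Share whose 12 weeks end before site start.** By cohort, (start − 8 − 2.76)/27 gives 0%, 8.3%, 26.8% and 45.3%.

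- 2, 4, 4, 2: (4 × .083 + 4 × .268 + 2 × .453)/12 = .193, or 96 of 500.
- 2, 2, 4, 4: (2 × .083 + 4 × .268 + 4 × .453)/12 = .254, or 127 of 500.

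**If Phase 1 enrolment were taken literally.** A client needs an enrolled clinician, and clinicians enrol from month 5. Opening at month 5 gives 3/30, 8/30, 13/30 and 18/30 by cohort, so 35.0% to 40.6% would be recruited before site start under the same two splits.

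**Dilution.** Assume that clients who finish before site start carry no between-condition effect, that all others carry the full effect, that the shares are equal in the two conditions, and that the standard deviation is unchanged. Then the estimated d is the true d × (1 − share).

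- .30 × (1 − .193) = .242
- .30 × (1 − .254) = .224

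C13a gives .30 as the smallest effect detectable in the client models at its 80% power criterion. Scaling from that point, power is Φ(2.80 × (1 − share) − 1.96), or about 62% to 55%. The simulation's full inputs are not given, so this is a scaling and not a re-run.

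**Under the Overview's rule, read site by site,** the share recruited before site start is zero and there is no dilution.

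**The case against.** The strongest reply is that the documents, taken together, lean towards site-by-site opening. Several parts of it stand.

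- Section V.C's window fits that reading. The first cohort would open at month 8 and the last ends at month 38, which forces a stop near month 35. The window does not say that every site recruits throughout.
- The Phase 1 heading over client screening cannot be a calendar limit, because screening by month 8 alone is impossible if recruitment runs to month 35. Phase labels are used loosely elsewhere: C12a attaches them to assessments timed from each cohort's own start.
- Section IX places a Phase 1 safety review ahead of client enrolment.
- The client procedures for weeks 0 to 11 in Section VII have clients follow the PHQ-9 schedule of their condition, which presupposes that the site has started. No procedure for waitlist clients is given.
- Figure 2 and the bars of Table 4, which has a client enrolment row, are not visible in the text available here and may show the timing.

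This is enough to reject the stronger reading that a reader might infer, namely that many later-cohort clients will certainly be analysed as treated before implementation. It does not remove the conflict. The Section VII summary still opens client enrolment in Phase 1, and the eligibility criteria and daily queries still admit any client of an enrolled clinician. If the mixed within- and between-subjects design named in the Specific Aims meant clients enrolled before site start to serve as controls, the model would need a period term, and it has none.

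A reader might also infer that clients recruited after their site's 15 months are unexposed. The documents do not support that: Section VII continues PHQ-9 collection under site guidelines for the rest of the funding period.

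**Conclusion.** The point holds as a contradiction that puts a co-primary comparison at risk. It does not show that the comparison is already compromised. Section V.C is compatible with either reading. The conflict is between the Phase 1 statements and open-ended eligibility on one side and the Overview on the other.

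On the all-sites reading, 28% to 34% of clients would be recruited before site start and 19% to 25% would complete 12 weeks before it, which would take a true d of .30 to an estimate of about .24 to .22. These figures rest on even accrual over months 8 to 35, two sites in the first cohort, and no between-condition effect in clients who finish early. The documents support only the second of these. The .30 is the plan's detectable effect and not a prediction of the result. On the Overview's reading the size is zero. The matter is more than wording, because the analysis plan has no safeguard if the first reading was followed.

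**What to change.** 1. Make the Overview's rule the single one: client enrolment opens at each site on that site's own implementation start date. Reconcile C12b, Section V.B, Section V.C, the Section VII Phase 1 summary and the Section VII client procedures to it.
2. State in C13a that the primary client-level comparison includes only clients whose baseline PHQ-9 is on or after their site's start date, with all enrolled clients analysed as a sensitivity analysis. Sites are randomized to early or later start and the same rule applies in both conditions, so the restriction does not favour either.
3. Do not exclude clients recruited after the site's 15 months.

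C13a is written partly in the past tense and reports 22.8% without the 12-week interview, so enrolment may already be complete. In that case the second step is the one that can still be taken, and it needs only recorded dates.

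The cost is fewer recruiting months at later sites. With a stop at month 35, a last-cohort site has 35 − 23 = 12 months instead of 27. Reaching the planned average of 42 clients there needs 42/12 = 3.5 a month against 42/27 = 1.6. The figure of over 30,000 depressed clients a year in C12b covers the whole organisation, so feasibility at these sites should be checked. If clients were already enrolled before site start, the cost is a smaller primary analysis set.
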